2.0 STUDY OBJECTIVES

Primary Objective

To compare the SherpaPak™ Cardiac Transport System to standard of care cold storage of donor hearts for transplantation.

Secondary Objective

To assess for a decrease in cold injury of donor hearts and therefore a decrease in primary graft dysfunction. To assess for events between study groups.

Primary Endpoint

The primary endpoint will be a composite endpoint of: Absence of moderate to severe primary graft dysfunction per ISHLT grading scale (left or right ventricle) in the first 24 hours post transplantation, and 30-day patient survival, 30-day incidence of ischemic reperfusion injury on endomyocardial biopsies and changes in mitochondria function and quality (at donor heart harvesting, at the time just prior to donor heart implantation and at one-week post- heart transplantation).

Secondary Endpoints – To describe between the groups

1. Each individual component of the composite endpoint will be assessed.
2. Hemodynamic parameters including cardiac index, cardiac output, blood pressure, mean arterial pressure, pulmonary artery pressure, left atrial pressure, right atrial pressure, right

ventricular pressure, stroke volume and ejection fraction at 24 hours post-transplant

3. The number of inotropes/pressors at 24 hours post -transplant.
4. Incidence of acute cellular rejection in the first 30 days post heart transplantation.
5. Incidence of antibody mediated rejection in the first 30 days post heart transplantation.
6. Incidence of heart graft related Serious Adverse Events in the first 30 days post heart transplantation.
7. Total length of stay
8. ICU length of stay
9. Number of blood products used

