6.0 DATA AND SAFETY MONITORING

6.1 DATA AND SAFETY MONITORING PLAN

Safety will be analyzed principally by examination of the frequency of adverse events. In particular, the number of donor heart graft-related serious adverse events (SAEs) up to the 30-day follow-up after transplantation per subject will be analyzed. This endpoint is defined to consist of the following adverse events (at most one per type), if they are serious adverse events:

- Primary heart graft dysfunction (not including rejection or cardiac tamponade):
 - Use of ECMO, RVAD, LVAD, BiVAD or insertion of a new IABP for >12 hours post TX.
 - Use of ≥ 2 inotropic agents/vasopressors including high-dose epinephrine or norepinephrine for >7 days post heart TX.
 - Open chest post heart TX. due to compromised heart function
- Primary graft failure requiring re-transplantation

Subjects will be monitored before, during and after the operative procedure to help ensure their safety. The investigators are members of transplant teams who have extensive experience with heart transplants and who will be trained to use the SherpaPak Cardiac Transport System to further minimize risk.

Subjects in the trial will undergo frequent visits and routine monitoring to help detect any abnormal changes and to provide appropriate treatment as necessary.

An independent Data and Safety Monitoring Board (DSMB) comprised of two expert heart failure physicians and one cardiothoracic surgeon not participating in the trial, will perform

monitoring activities to ensure the identification, documentation, and analysis of adverse events; and to ensure compliance with the protocol and procedures that are in place for conducting research to protect the safety and well-being of all subjects. The DSMB will have a formal meeting at least once annually. Frequency of the meetings may be changed by the DSMB in consultation with the Principal Investigator based on need. An ad hoc meeting may be called at any time by the Chairperson or by the PI and research staff should ethical or patient safety issues arise.

A status update will also be provided to the DSMB on a quarterly basis via email correspondence by the DSMB Coordinator.

The criteria below provide guidance for suspending trial enrollment/randomization until review by the DSMB. Selected serious adverse events (SAEs) of concern and their thresholds are:

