- Two (2) episodes of severe primary graft dysfunction (PGD) per ISHLT grading criteria (left or right ventricle, not including rejection or cardiac tamponade) requiring use of a mechanical circulatory support (MCS) device within 24 hours after transplant in subjects randomized to the SherpaPak method of transport.
- Two (2) deaths occur in subjects randomized to the SherpaPak method of transport within 7 days after transplant.

It is the responsibility of the Principal Investigator to report all of the above SAEs to the DSMB within 24 hours of discovering the event.

In the event that the study is suspended, no new subjects will be consented or randomized to the trial. Subjects already in follow-up on the study will continue to be followed as outlined in the protocol unless the appointed Chair provides further recommendations.

All heart graft-related adverse events and serious adverse events are to be recorded on the electronic case report forms until post-transplant day 30. The description of the adverse event will include: the date of onset, duration, severity, seriousness, the relationship of the event to the trial treatment, anticipated or not, and any treatment required. All serious adverse events occurring during the course of the first 30 days post-transplant will be documented on the appropriate electronic case report form(s) in REDCap. Heart graft-related AEs will be recorded up to the 30-day follow-up or through hospital discharge if longer than 30 days. The principal investigator is responsible for the classification and reporting of heart graft-related adverse events to the appropriate regulatory authorities.

A SAE is any AE that in the view of the Investigator results in death, is life-threatening, requires inpatient hospitalization or causes prolongation of existing hospitalization. In the interest of patient safety, and in order to fulfill regulatory requirements, all SAEs (regardless of their relationship to the study procedures) will be documented and reported per IRB guidelines. In the interest of this study, the SAEs that meet the stopping rule criteria within the DSMB Charter, will be submitted to the DSMB for review.

Heart-graft related-AEs will be captured in this study. The investigator will assess the relationship of the AE to the SherpaPak Cardiac Transport System or to the standard of care methods of preservation. The relationship will be assessed using the following categories:

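### Section 6.1 counts a listed graft event in the SAE endpoint only if the investigator also judges it serious, which adds avoidable discretion, mainly for new balloon pump, prolonged inotropes/vasopressors and open chest (minor)

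*Combined protocol and SAP*

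**What the plan says.** Secondary endpoint 6 in section 2.0 is "Incidence of heart graft related Serious Adverse Events in the first 30 days post heart transplantation". Section 6.1 gives the matching safety count, per subject up to the 30-day follow-up, and defines it by a list: mechanical support (ECMO, ventricular assist device, or a new balloon pump for more than 12 hours); two or more inotropes/vasopressors, including high-dose agents, for more than 7 days; a chest left open because of poor heart function; and graft failure leading to re-transplantation. The list opens with a condition: "This endpoint is defined to consist of the following adverse events (at most one per type), if they are serious adverse events".

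Further on, section 6.1 defines an SAE as "any AE that in the view of the Investigator results in death, is life-threatening, requires inpatient hospitalization or causes prolongation of existing hospitalization". On who decides, it says "The principal investigator is responsible for the classification and reporting of heart graft-related adverse events", and "The investigator will assess the relationship of the AE to the SherpaPak Cardiac Transport System or to the standard of care methods of preservation". On independent review, it says "the SAEs that meet the stopping rule criteria within the DSMB Charter, will be submitted to the DSMB for review".

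Sections 7.1 and 7.2 plan summary statistics and mainly descriptive comparisons. No test, error rate or power is attached to this endpoint.

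**The concern.** Meeting a listed definition is not enough for an event to count. It must also pass a seriousness test that rests on opinion, and the person giving the opinion very probably knows how the heart was transported. If that person is slightly readier to call an event serious in one arm than in the other, the endpoint will show a difference that the hearts did not. Because the comparison is descriptive and the arms are small, readers will take the raw counts at face value. The condition also buys little, since seriousness is already a separate item in the adverse event description that section 6.1 requires.

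**Working it through.** The plan gives no event rate or sample-size derivation for this endpoint, so there is no stated figure to reproduce. The check is a reading of the rules, followed by an illustration of size.

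**Reading the rules together**

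1. *Is a listed event serious by definition?* No. The condition in section 6.1 presupposes that some listed events will not be SAEs, and no other section says otherwise.
2. *Who decides seriousness?* The investigator: "A SAE is any AE that in the view of the Investigator results in death, is life-threatening". No masked adjudication is described.
3. *Does that person know the arm?* The documents do not say so. They describe no masking, however, and they require a judgement of relatedness to the preservation method, using categories all worded in terms of the SherpaPak. The investigators are also transplant team members who will be "trained to use the SherpaPak Cardiac Transport System to further minimize risk". Knowledge of the arm is therefore a strong inference.
4. *Which seriousness criteria can discriminate?* During the transplant admission the recipient is already an inpatient, so a need for admission separates nothing. A non-fatal event then turns on whether it threatened life or lengthened the stay, and no expected stay is given for comparison.
5. *Which listed events are open to judgement?* ECMO, a ventricular assist device and re-transplantation would nearly always be called life-threatening. A new balloon pump, a long inotrope/vasopressor course and an open chest leave more room.
6. *Does independent review close the gap?* The DSMB has a general monitoring role. The SAEs that section 6.1 says will be submitted to it are those meeting the stopping criteria, which are severe graft dysfunction needing mechanical support within 24 hours and death within 7 days, both in the SherpaPak arm only. No step re-examines seriousness for the three event types above.

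**Size of one dropped event**

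Section 3.4 randomizes 1:1. Section 4.0 gives about 20 subjects, worded so that it can mean 20 in total (10 per arm) or 20 per arm. If a subject's only counted event is dropped, the arm's incidence moves by 1/n:

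- n = 10: 1/10 = 10 percentage points
- n = 20: 1/20 = 5 percentage points

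If the subject has another counted event, incidence does not move.

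**Illustrative artefact**

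Assume the same true risk p of a listed event in both arms, at most one event per subject, control events always called serious, and device-arm events called serious with probability s. The values of p and s are assumptions; the documents give none. The direction is also an assumption and could be reversed.

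- Apparent difference = p − p·s = p(1 − s)
- Chance of at least one dropped device-arm event = 1 − [1 − p(1 − s)]^n

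| p | s | p(1 − s) | chance, n = 10 | chance, n = 20 |
|---|---|---|---|---|
| 0.1 | 0.9 | 1 point | 0.096 | 0.182 |
| 0.2 | 0.8 | 4 points | 0.335 | 0.558 |
| 0.3 | 0.7 | 9 points | 0.611 | 0.848 |
| 0.4 | 0.5 | 20 points | 0.893 | 0.988 |

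Over p from 0.1 to 0.4 and s from 0.5 to 0.9, the apparent difference runs from 1 to 20 points. If every listed event counts whenever its definition is met, s drops out and this part of the artefact is 0.

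**The case against.** The strongest reply is that the discretion is narrow and mostly harmless. Several listed events would pass any seriousness test. That stands, and it confines the point to the three event types named above. A reader might infer that any device use could count in one arm and not in the other; for ECMO and ventricular assist devices that is not a realistic reading.

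Second, much of the same information is captured without the filter. Sections 4.1 and 5.3 collect mechanical support and inotrope data regardless of seriousness, section 5.3 collects graft survival, graft dysfunction by ISHLT grade is part of the primary composite and reported separately (section 2.0), and section 6.1 records non-serious graft-related events too. This also stands: an excluded event is not lost and could be re-counted. But the endpoint as defined does not use those data. Open chest is not a named variable in section 5.3, and the timed inotrope doses there stop at 72 hours, well short of the 7-day criterion.

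Third, removing the condition does not make the count free of judgement. Attribution of an open chest to heart function, the exclusion of rejection and tamponade, and a high-dose criterion without a threshold all remain with the investigator. That is correct; the fix removes one layer of discretion, not all of it.

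Fourth, a reader might take a figure such as 9 points as the expected bias. It follows from invented rates and, with 10 per arm, is less than one patient (0.09 × 10 = 0.9). It illustrates the mechanism and estimates nothing.

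**Conclusion.** The point holds, as a minor one. A stated rule adds avoidable and potentially arm-dependent discretion to secondary endpoint 6. The conclusion rests on reading that endpoint as the count defined in section 6.1, which the shared label and 30-day window support, and on the inference that the assessor knows the arm.

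The firm figure is the shift from one dropped subject: 10 points with 10 per arm or 5 points with 20 per arm. The 1 to 20 point range is conditional on the assumed rates.

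Three stronger readings are not supported:

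- That differential counting will occur. The documents show only that it can.
- That the whole safety analysis or the primary composite is compromised. Section 6.1 bases safety mainly on adverse event frequency, with this count singled out within it, and the primary composite carries no seriousness filter.
- That the SAE definition must be widened, for example to lasting impairment. The documents cite no standard requiring it, and it would not affect this endpoint once listed events count on their own definitions.

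**What to change.** In section 6.1, delete the closing clause that makes seriousness a condition for the listed events. State instead that each listed event counts in the endpoint whenever its definition is met, at most once per type, and that the investigator's seriousness call is reported separately. Point secondary endpoint 6 in section 2.0 to that list, so that its label is not read as restoring the filter. The SAE criteria themselves need no change for this purpose.

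The cost is a wording change, with no added visits, subjects or tests; seriousness is already recorded. A few borderline events may be added in both arms, and the attribution judgements inside the listed definitions remain.

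### As the protocol is written, a non-fatal early MCS event in the SherpaPak arm that the investigator attributes to rejection or tamponade need not reach the DSMB promptly, although that attribution can decide whether the suspension criterion is met.

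*Combined protocol and SAP*

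**What the plan says.** Section 6.1 (Data and Safety Monitoring Plan) gives two criteria as guidance for suspending enrolment and randomization until the DSMB has reviewed.

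- **Graft criterion.** "Two (2) episodes of severe primary graft dysfunction (PGD) per ISHLT grading criteria", left or right ventricle, qualified as "not including rejection or cardiac tamponade) requiring use of a mechanical circulatory support (MCS) device within 24 hours after transplant", in subjects randomized to SherpaPak.
- **Death criterion.** "Two (2) deaths occur in subjects randomized to the SherpaPak method of transport within 7 days after transplant". No cause of death is excluded.

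Three reporting provisions follow in the same section.

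- **Expedited report.** "It is the responsibility of the Principal Investigator to report all of the above SAEs to the DSMB within 24 hours of discovering the event".
- **Submission to the board.** In the interest of the study, "the SAEs that meet the stopping rule criteria within the DSMB Charter, will be submitted to the DSMB for review".
- **All other SAEs.** "all SAEs (regardless of their relationship to the study procedures) will be documented and reported per IRB guidelines". The DSMB is not named as a recipient here.

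On who classifies events, Section 6.1 states: "The principal investigator is responsible for the classification and reporting of heart graft-related adverse events to the appropriate regulatory authorities". The investigator also rates how each graft-related event relates to the transport method. The board consists of two heart failure physicians and one cardiothoracic surgeon who take no part in the trial. It meets formally at least once a year, receives a quarterly e-mail update whose content is not specified, and can be convened ad hoc.

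**The concern.** The order of steps is the difficulty. Rejection and tamponade are removed inside the definition of the countable event, and the duty to report within 24 hours attaches to the event as defined. The investigator's attribution therefore comes before the report and determines whether there is one. The protocol does not ask anyone independent to look at that attribution before the count is set.

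Excluding other causes from a definition of primary graft dysfunction is a reasonable choice and is not criticised here. But the attribution takes judgement. The documents give no criteria for it, and the schedule in Section 4.1 places the first recipient endomyocardial biopsy at Day 7 ± 2 days, so no scheduled biopsy informs a call made in the first 24 hours.

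At stake is the timing of a safety review. If an event is wrongly left out and the count stays at one, later subjects may be randomized before the board has had a chance to look.

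**Working it through.** **Step 1: follow one event through the text.** Take a SherpaPak subject who needs an MCS device within 24 hours and survives beyond 7 days, where the investigator attributes the event to tamponade.

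| Provision | Does it require prompt notice to the DSMB? |
|---|---|
| Graft criterion (6.1) | No, the event is excluded by definition |
| Death criterion (6.1) | No, the subject survived |
| 24-hour report (6.1) | No, it covers the listed SAEs |
| Submission clause (6.1) | No, it refers to SAEs meeting the Charter's stopping criteria |
| All-SAE clause (6.1) | No, it is documented and reported per IRB guidelines |
| Quarterly e-mail (6.1) | Not stated, the content is unspecified |
| Annual or ad hoc meeting (6.1) | Not stated; an ad hoc meeting depends on someone raising the issue |
| Internal auditor (6.2) | No, the role covers adherence and data accuracy |

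**Step 2: is the person attributing masked?** No masking is described. Investigators are trained on the device and rate relatedness to the transport method. That they know the arm is an inference, though a strong one.

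**Step 3: how much can one attribution matter?** The plan states no event rate and no operating characteristic for the suspension rule, so there is no figure to reproduce. The following is illustration.

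Inputs:
- Threshold: 2 (Section 6.1).
- SherpaPak subjects: n = 10, reading Section 4.0's approximately 20 as the total under 1:1 randomization (Section 3.4). The word *respectively* in Section 4.0 also allows 20 per arm, so n = 20 is shown too.
- p, the true rate of qualifying events: assumed.
- m, the share of true events wrongly attributed to rejection or tamponade: assumed.

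With q = p(1 − m), the chance of at least two counted events is 1 − (1 − q)^n − n·q·(1 − q)^(n−1).

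For n = 10 and p = 0.20:
- m = 0: q = 0.20; 1 − 0.107 − 0.268 = 0.624
- m = 0.10: q = 0.18; 1 − 0.137 − 0.302 = 0.561
- m = 0.25: q = 0.15; 1 − 0.197 − 0.347 = 0.456
- m = 0.50: q = 0.10; 1 − 0.349 − 0.387 = 0.264

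| n | p | m = 0 | m = 0.10 | m = 0.25 | m = 0.50 |
|---|---|---|---|---|---|
| 10 | 0.10 | 26% | 23% | 17% | 9% |
| 10 | 0.20 | 62% | 56% | 46% | 26% |
| 10 | 0.30 | 85% | 80% | 69% | 46% |
| 20 | 0.10 | 61% | 55% | 45% | 26% |
| 20 | 0.20 | 93% | 90% | 82% | 61% |

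**Step 4: the marginal case.** If exactly two true events occur, both must be counted, so the criterion is met with probability (1 − m)²: 0.81, 0.56 and 0.25 for m = 0.10, 0.25 and 0.50, taking the attributions as independent.

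**Step 5: how long might a delay last?** Section 5.2 gives a data window of 24 months (September 2021 to August 2023). With 20 subjects and even accrual (an assumption), 20 × 3/24 = 2.5 subjects are randomized between quarterly e-mails and 20 × 12/24 = 10 between annual meetings, both arms together. These double if 20 per arm is meant.

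**The case against.** The strongest reply is that the governing text may lie elsewhere. The submission clause points to the DSMB Charter, which is not among the documents and could require wider reporting or adjudication. That stands, and it limits the conclusion to what the protocol itself requires.

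Other safeguards also exist. The board has a general duty to ensure that adverse events are identified, documented and analysed. All SAEs to day 30 go on the electronic case report form, MCS data are collected for every subject, and deaths within 7 days count whatever their cause. These make it unlikely that an event would stay unseen for good. None of them requires the board to see a non-fatal excluded event promptly.

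The illustration is open to challenge too. The misattribution shares are assumed, and at 10% the loss is modest. If the excluded events really were rejection or tamponade, a lower count is what the rule intends and there is no harm. Both points stand.

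A reader might infer more than the text supports:
- *That the board is barred from seeing these events.* It is not. The submission clause contains no word limiting submission to such events alone, and other channels are open.
- *That the Principal Investigator has an interest in attributing events away.* The documents describe no such interest. The study is internally funded and both methods are described as FDA approved. The sentence making that person responsible for classification concerns reporting to regulatory authorities, not the suspension count.

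Finally, investigator classification against a named scale under DSMB oversight is a coherent choice for a small descriptive pilot. That is fair, and it is why this is a suggestion and not an error in the plan.

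**Conclusion.** The point holds as a gap in the protocol's reporting rule, subject to the unseen Charter. The protocol does not require prompt notice to the DSMB of a non-fatal SherpaPak MCS event within 24 hours once it has been attributed to rejection or tamponade, and it provides no independent check of that attribution. With a guidance threshold of two, a single attribution can decide whether the criterion is met, but only when the count is at the margin.

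The textual finding does not depend on any event rate. The size does: at n = 10 and an assumed 20% true rate, the chance of meeting the criterion falls by about 6, 17 or 36 percentage points as 10%, 25% or 50% of true events are wrongly attributed. The documents give no evidence that misattribution would occur at any of these levels, and the figures should not be read as a forecast. Importance is low, and the point is worth acting on because the remedy is cheap.

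**What to change.** Leave the threshold and the exclusion as they are. Change the reporting sentence in Section 6.1 to read along these lines:

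*Every use of an MCS device within 24 hours after transplant in a subject randomized to SherpaPak, whatever the attributed cause, and every death meeting the second criterion, is reported to the DSMB within 24 hours of discovery. MCS reports include the investigator's proposed cause and supporting findings, and the DSMB confirms whether the event counts toward the first criterion.*

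The trigger should be MCS use as such. If it were MCS use for severe graft dysfunction, the investigator's judgement of cause would again decide what is reported. Keeping the sentence to the SherpaPak arm matches the existing criteria and adds no expedited reporting for control subjects. Align the Charter if it differs; if it already requires this, a cross-reference in Section 6.1 is enough.

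The cost is one reworded sentence, a few additional reports, and a small confirmation task for a board that is already appointed and has the relevant expertise.

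### Section 6.1 requires no prompt report to the DSMB of SherpaPak deaths on Days 8-30 or of re-transplantation for primary graft failure

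*Combined protocol and SAP*

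**What the plan says.** Section 6.1 introduces the criteria as follows: "The criteria below provide guidance for suspending trial enrollment/randomization until review by the DSMB". There are two, both confined to the SherpaPak arm:

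- The first counts graft dysfunction: "Two (2) episodes of severe primary graft dysfunction (PGD) per ISHLT grading criteria", further limited to episodes "requiring use of a mechanical circulatory support (MCS) device within 24 hours after transplant in subjects randomized to the SherpaPak method of transport".
- The second criterion counts early mortality and reads: "Two (2) deaths occur in subjects randomized to the SherpaPak method of transport within 7 days after transplant".

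The next sentence makes the principal investigator report the SAEs listed above to the DSMB within 24 hours of discovery. Later in the same section, "the SAEs that meet the stopping rule criteria within the DSMB Charter, will be submitted to the DSMB for review". All SAEs, whatever their cause, are also to be reported under IRB guidelines, with no timing given.

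Earlier in 6.1, the graft-related SAE endpoint runs to the 30-day follow-up. Its listed events include "Primary graft failure requiring re-transplantation" and "Use of ≥ 2 inotropic agents/vasopressors including high-dose epinephrine or norepinephrine for >7 days post heart TX". In section 2.0, the primary endpoint includes "30-day patient survival".

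The DSMB's other sources of information, also in 6.1, are a formal meeting at least once a year, a quarterly e-mail update whose content is not described, and ad hoc meetings that the Chairperson or the study team may call.

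**The concern.** The outcomes that the trial itself treats as central run to Day 30, but the duty to tell the DSMB promptly follows the two suspension criteria. A SherpaPak subject who dies on Day 9, or is re-transplanted on Day 12, has had an event of the kind the trial is set up to count. Neither outcome falls under the 24-hour report as written.

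The ad hoc meeting is the natural safeguard. However, the Chairperson can call one only if informed, and 6.1 obliges nobody to inform the Chairperson promptly of these outcomes. In a trial of about 20 subjects, each such event is a large share of the evidence on safety, and randomization could continue for weeks or months before the board saw it.

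**Working it through.** The plan gives no event risks and no operating characteristics for its criteria, so there is no figure to reproduce. The check has two parts.

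**1. Which outcomes carry a required prompt DSMB report (section 6.1)**

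| SherpaPak outcome | In the trial's own endpoints? | Suspension criterion | Required 24-hour DSMB report |
|---|---|---|---|
| Severe PGD, mechanical support within 24 h | Yes | Yes (two episodes) | Yes |
| Death by Day 7 | Yes | Yes (two deaths) | Yes |
| Death on Days 8-30 | Yes (30-day survival) | None | None |
| Re-transplantation for primary graft failure | Yes (graft-related SAE) | None | None, unless the SAEs listed above is read to reach back to the graft-SAE list |

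Two readings matter here. First, I take a single listed event to be reportable, because the duty runs from discovery of the event rather than from reaching a count of two. Second, the reporting sentence directly follows the two criteria, and the later sentence refers to stopping-rule criteria. Both favour the narrow scope over the longer SAE list.

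**2. How often the DSMB would receive no 24-hour report at all**

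Inputs: 1:1 randomization (section 3.4) and about 20 subjects (section 4.0), so n = 10 on SherpaPak. The wording of 4.0 could also mean 20 per arm, so n = 20 is shown as well. Per-subject risks are assumptions, in exclusive categories:

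- A: severe PGD on mechanical support
- B: other death by Day 7
- C: death on Days 8-30, or re-transplantation, with neither A nor B

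Let e = 1 − A − B − C be the risk of no such event. The chance of two or more C events with no A or B event is

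(C + e)^n − e^n − n·C·e^(n−1).

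For n = 10:

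- A 10%, B 5%, C 5%: 0.85^10 − 0.80^10 − 10(0.05)(0.80^9) = 0.197 − 0.107 − 0.067 = 0.022
- A 5%, B 3%, C 5%: 0.92^10 − 0.87^10 − 10(0.05)(0.87^9) = 0.434 − 0.248 − 0.143 = 0.043
- A 5%, B 5%, C 10%: 0.90^10 − 0.80^10 − 10(0.10)(0.80^9) = 0.349 − 0.107 − 0.134 = 0.107 (unrounded terms)

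The range is therefore 2.2% to 10.7%. The same formula with n = 20 gives 1.3%, 5.6% and 8.1%.

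**Time to routine review.** If accrual is even over the 24-month data window in section 5.2 (an assumption), 10 × 12/24 = 5 SherpaPak subjects are transplanted between annual meetings, or 10 if there are 20 per arm. Quarterly e-mails fall in between.

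**The case against.** The criteria are presented as guidance on selected events, not as a complete list. An ad hoc meeting can be called at any time, the DSMB can change its meeting frequency, quarterly updates are sent, and every SAE goes to the IRB. The Charter is not among the documents and may contain more. All of this stands, and it limits the point to what 6.1 itself requires.

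From the same text a reader might infer three stronger things, none of which the documents support.

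- **That several SherpaPak subjects could lose the graft or die with no pause and no report of any kind.** This overlooks the discretionary and IRB routes. It also overlooks that a subject with severe PGD on support in the first 24 hours who dies on Day 9 has already been reported and counted for the PGD. Only the death itself goes without a required prompt report.
- **That the 7-day death window contradicts the 30-day endpoint or the graft SAE that needs more than 7 days, or that separate counting is an error.** A suspension trigger need not share the endpoint's horizon. An early window and separate counts are defensible design choices.
- **That the gap is large in probability.** Under the same assumed risks (n = 10), the chance that two or more subjects have any A, B or C event while neither criterion is met is 29%, 26% and 46%. But most of those cases contain a listed event already reportable within 24 hours: from 1 − 0.107/0.457 = 77% to 1 − 0.022/0.291 = 92%. Those figures do not measure what goes unreported.

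**Conclusion.** The point holds in a limited form. As 6.1 is written, deaths on Days 8-30 and re-transplantations for primary graft failure meet no suspension criterion and carry no required prompt report to the DSMB, although both belong to the trial's own 30-day outcomes. That conclusion rests on the text and needs no assumed risk. It does depend on reading the 24-hour duty as covering only the two criteria that precede it, and the Charter could change it.

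The size is illustrative only: about 2% to 11% for two or more such events with no 24-hour report at all, with 10 SherpaPak subjects and the risks assumed above. This is a gap in reporting to the DSMB. It does not show that the suspension thresholds are wrong. It should be closed because the change is cheap and the board cannot use its ad hoc powers on events it has not been told about.

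**What to change.** In section 6.1, extend the investigator's 24-hour report to the DSMB to every death through Day 30 and every re-transplantation for graft failure. State exactly which events the reporting sentence covers, and reconcile that wording with the graft-related SAE list earlier in 6.1, the later sentence on stopping-rule criteria, and the Charter. Leave suspension thresholds, their time windows and any combined counting to the DSMB.

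The cost is wording in the protocol and the Charter, a few extra e-mails, and possibly one more ad hoc review. No new data are needed, because 6.1 already has all SAEs in the first 30 days recorded in REDCap.
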